Date: April 9, 2019

Title: Importance of Sock Type in the Development of Foot Lesions on Low-difficulty, Short Hikes.

Description of document: Materials and Methods (Study Protocol: description of the clinical study, including objective and design. Statistical Analysis Plan (description of the statistical considerations for analyzing the data collected in the study.) results of the study (Results obtained in the study) and Supplementary data (protocol of measures and other tables).

Materials and Methods

1. Permission and participants

All participants signed an informed consent form, and permission for the study was obtained from the Bioethics Committee (reference 126/2016). The admission criteria were: be of legal age, have no current health problems that would hinder or prevent participation in the hike, and carry a backpack weighing less than 3 kg. Participants were asked to use specific hiking footwear (light, flexible, soft-soled, with good grip and breathable material) (low top hiking shoes), based on earlier studies [38-40]. They were also asked to do the entire hike following the instructions of an experienced guide and to not remove their footwear or socks before examination by a podiatrist.

2. Sock type and interventions performed

Socks were of two types: technical socks, designed for high performance sports use (Lurbel brand, models Tierra and Set), and non-technical socks for everyday use. The socks had different composition: Tierra (50% regeneractiv, 25% cool-teak, 17% polyamide ions, 8% lycra); Set (75% cotton, 17% polyamide, 8% lycra) and cotton (98% cotton, 2% elastane). The technical socks had reinforced weave in the toe, metatarsal and heel areas.

Participants were examined by trained podiatrists on three occasions to measure the study variables: at the start of the walk (km 0), at the end of the asphalt section (half way; km 14.5) and at the end (km 29.6). The protocol of measures was followed (supplementary data).

3. Study design, route description and participants

Weight (kg)

A clinical trial randomized, double blinded was designed to analyze the influence of different types of socks (technical and non-technical) on the appearance of foot injuries after a low-difficulty, short-term sport activity. The study follow the CONSORT criteria.

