To carry out the study, the hiker was previously registered. The researchers contacted the participants to explain the study. In addition, data on age, sex, foot number and associated diseases that prevented the completion of the route were obtained. One hour before starting the route, researchers who did not intervene in the exploration process, made registration and delivery to each hiker of two technical socks (1 Set and 1 Tierra) appropriate to the size of the foot and randomly for the right foot (RF) and left foot (LF). Likewise, it proceeded for non-technical socks (cotton), but in this case both feet wore the same type of sock. All the participants before the initial exploration had their socks put on for half an hour. The hike was low-difficulty, over a short distance [37]. The first 14.5 km were on asphalt and the last 15.1 km on dirt. The height range was 189 m and the pace was moderate, at 5 km/hour. The sample comprised 109 participants (53 men and 56 women). Two women had to give up the hike for personal reasons. Both wore technical socks.

The Table 1 explain the anthropometric characteristics of the participants and the distribution of the socks, differentiating by sex and feet.

Anthropometric variable	Total	Male	Female	
Gender		48.6%	51.4%	
Age (years)	44± 25	49± 21	36 ± 24	
Height (meters)	1.7± 0.1	1.7± 0.1	1.6± 0.1	

81.0±13.5

61.4±7.8

68.8±19.4

Table 1. Anthropometric variables, total sock distribution and sock distribution by gender.

BM	II	24.9± 3.6	26.6± 3.7	23.5± 9.1
Sock type di	istribution	Total %	Male %	Female %
LF sock	Tierra	40.4 (n=44)	35.8 (n=19)	44.6 (n=25)
	Set	29.4 (n=32)	35.8 (n=19)	23.3 (n=13)
	Cotton	30.2 (n=33)	28.4 (n=15)	32.1 (n=18)
RF sock	Tierra	29.4 (n=32)	35.8 (n=19)	23.3 (n=13)
	Set	40.4 (n=44)	35.8 (n=19)	44.6 (n=25)
	Cotton	30.2 (n=33)	28.4 (n=15)	32.1 (n=18)

Km=Kilometres, n=sample size, %=Percentage, ±=Standard deviation, kg=Kilogrammes, BMI=Body mass index, LF=Left foot, RF=Right foot.

4. Study variables

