The differences in temperature are greater at the beginning of the hike than at the end. An increase in temperature from 0 km to 14.5 km was observed, and temperature stabilization of 14.5 km to 29.6 km in all types of socks. However, the increase in temperature, from the beginning to the end of the hike, varies between the types of socks in all the areas measured at the foot of the walkers; being superior when using non-technical socks (about 8.5°C) than in the case of using technical socks (about 1.2°C) (Supplementary data, tables A, B).

Table 5. Women's foot temperature by sock type.

					FEMAL	E			
Distance	Sock P-value sock			P-	value distanc	e			
(km)	Т	S	С	T-S	T-C	S-C	T	S	С
				Dor	sal temp (°C) RF			
0	34.7	35.0	19.9	1.000	0.000*	0.000*	(1)=0.002*	(1)=0.000*	(1)=0.001*
14.5	36.2	36.3	31.8	1.000	0.013*	0.000*	(2)=0.000*	(2)=0.000*	(2)=0.000*
29.6	36.3	36.3	30.6	1.000	0.000*	0.000*	(3)=1.000	(3)=1.000	(3)=0.867
				Dor	sal temp (°C) LF			
0	35.0	35.0	19.9	1.000	0.000*	0.000*	(1)=0.000*	(1)=0.005*	(1)=0.003*

14.5	36.4	36.2	32.2	0.931	0.002*	0.036*	(2)=0.000*	(2)=0.001*	(2)=0.000*
29.6	36.3	36.3	30.8	1.000	0.000*	0.000*	(3)=1.000	(3)=1.000	(3)=0.472
				Plan	tar temp ((ºC) RF			
0	34.8	34.8	20.5	1.000	0.000*	0.000*	(1)=0.007*	(1)=0.000*	(1)=0.000*
14.5	36.0	36.2	29.7	1.000	0.000*	0.000*	(2)=0.001*	(2)=0.000*	(2)=0.000*
29.6	36.2	36.2	30.6	1.000	0.000*	0.000*	(3)=1.000	(3)=1.000	(3)=1.000
				Plan	tar temp	(ºC) LF			
0	34.8	34.9	21.0	1.000	0.000*	0.000*	(1)=0.002*	(1)=0.009*	(1)=0.000*
14.5	36.2	36.0	30.2	0.287	0.000*	0.000*	(2)=0.000*	(2)=0.000*	(2)=0.000*
29.6	36.1	36.0	30.2	1.000	0.000*	0.000*	(3)=0.420	(3)=0.785	(3)=1.000

Km=Kilometres, T=Tierra, S=Set, C=Cotton, Temp=Temperature, (°C)=Degrees centigrade, RF=Right foot, LF=Left foot, (*)=Significant difference, (1)= Distance between 0-14.5 Km, (2)= Distance between 0-29.6 Km, (3)= Distance between 14.5-29.6 Km.

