The study of the perimeter of hikers' feet analysed in total and by gender, in relation to distance and sock type, did not reveal significant results (data not shown).

Table 7. Probability of suffering skin and muscle lesions in relation to anthropometric variables and sock type throughout the hike.

1	PROBABILITY SKI	N LESIONS	PROBABILITY M	USCLE LESIONS		
Dist	ance:	Distance: 14.5-29.6 Km	Distance: 0-14.5 Km			
96% If	female	90% If male	100% I	f male		
100% If non-	technical sock	100% If non-technical sock	67% If non-te	chnical sock		
Direct relation	Inverse relation	Inverse relation	Direct relation	Inverse relation		
BMI	Age	Age	BMI	Age		

km=Kilometre, %= Percentages, BMI=Body mass index.

It was possible to study the relation between variables and predict the probability of lesions developing during the hike using logistic regression analysis (Table 7). Women have a higher probability than men of suffering skin lesions in hikes of up to 14.5 km. However, men have a higher probability than women of suffering skin lesions on hikes of 14.5 to 29.6 km and muscle lesions on hikes of up to 14.5 km.

The non-technical socks showed the highest probability of wearers suffering dermal and muscle lesions, both from 0-14.5 km and from 14.5 km to the end of the hike. The probability of dermal and muscle lesions developing in relation to the quantitative variables showed direct and inverse relations. From 0-14.5 km, the BMI and age of hikers are directly and inversely related, respectively, both in dermal and in muscle lesions. In the second part of the hike, age continued to show an inverse relation with skin lesions, but no relation with BMI was identified (Table 7).

Supplementary data

Protocol of Measures. Top shows the protocol of measure at the starting point (0 km). Middle part includes the protocol of the first part of the hike (0-14.5 km) and lower part of the table reflex the measurement protocol of the second part of the hike (14.5-29.6 km)

PPOTOCOI	OF MEASURES
STARTING POINT (0 Km)	OF MEASURES
Dorsal Number: Gender: Gender:	Foot size Weight Size
Body mass index (BMI):	The state of the s
	Previous Alterations on skin, muscles or
nails	
	rature LF
Plantar Plantar	
Dorsal Dorsal	
Perimeters RF: (Three different measures)	Perimeters LF: (Three different measures)
tibia	tibia
hell	hell
toes instep	toes instep
FIRST PART OF THE HIKE (0-14.5 Km)	Perimeters RF: (Three different measures)
	tibia
Temperature RF: (Three different measures)	
Plantar	

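### The text after Table 7 words two sections of one fixed-order hike as hikes of two lengths, which this design cannot separate from surface, order or the mid-route stop

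*Combined protocol and SAP*

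**What the plan says.** The route is given in Materials and Methods, section 3: "The first 14.5 km were on asphalt and the last 15.1 km on dirt". Section 1 has every participant walk all of it: "They were also asked to do the entire hike following the instructions of an experienced guide". Section 2 places the second and third examinations "at the end of the asphalt section (half way; km 14.5) and at the end (km 29.6"), so the middle one falls exactly where the surface changes.

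The measurement form in the supplementary data has one lesion block for km 0-14.5 and another for km 14.5-29.6. Tables 3 and 4 report these blocks as parts of the hike.

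The text after Table 7 uses different terms. It states "Women have a higher probability than men of suffering skin lesions in hikes of up to 14.5 km", and then, introduced by 'However', that "men have a higher probability than women of suffering skin lesions on hikes of 14.5 to 29.6 km". No limitation for surface, order or the stop is stated anywhere in the document.

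**The concern.** Read as written, the two sentences say that the sex with the higher risk of skin lesions depends on how long the hike is. No group walked a different length, took the surfaces in the other order, or went without the mid-route examination. Anything that differs between the sections could be due to dirt rather than asphalt, to accumulated walking, to lesions already present, or to the stop.

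Several reported changes are open to the same reading by length. Skin lesions go from 6.6% to 21.1% in technical socks and from 36.4% to 54.8% in cotton. Pain from inadequate warm-up goes from 21.1% to 11.2%. Reddened skin, urticaria, crevice and heloma appear only in the second section.

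**Working it through.** **1. Route.** 14.5 + 15.1 = 29.6 km. At the stated 5 km/h the sections take 14.5/5 = 2.9 h and 15.1/5 = 3.0 h. They are of nearly equal length, so the second is not a longer hike than the first.

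**2. What can be separated.** Code each hiker's two sections:

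| Section | Distance | Surface | Order | After the stop |
|---|---|---|---|---|
| First | 0 | 0 | 0 | 0 |
| Second | 1 | 1 | 1 | 1 |

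The four columns are identical. With an intercept, the matrix has rank 2 out of 5 columns. Adding sex and its interaction with each factor gives rank 4 out of 10. The data carry one between-section contrast, and one change in the sex effect, for all four factors together. No reanalysis can divide them.

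**3. What the second label counts.** Take left-foot blisters in women wearing cotton. Table 3 gives 27.8%, which is 5/18. Table 4 gives 12.5%, which is 2/16. A cumulative count could not fall this far: even if both women who withdrew were among the five, at least 3/16 = 18.8% would remain. The counts are therefore per section. The risk over the whole hike would be the proportion with a lesion in either section, and that is not reported.

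**4. Reproducing the reported tests.** Counts are rebuilt from the percentages, with two-sided Fisher tests:
- First section by sex: 13/56 = 23.2% against 4/53 = 7.5%, p = 0.0337 (stated 0.034).
- Second section by sock: 16/76 = 21.1% against 17/31 = 54.8%, p = 0.0011 (stated 0.001).
- Second section, women by sock: 10/38 = 26.3% against 11/16 = 68.8%, p = 0.0057 (stated 0.006).

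The rebuilt counts match the document's own results.

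**5. Sex in the second section.**
- Technical: women 10/38 = 26.3%, men 6/38 = 15.8%.
- Cotton: women 11/16 = 68.8%, men 6/15 = 40.0%.
- Together: women 21/54 = 38.9%, men 12/53 = 22.6%, Fisher p = 0.094.

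For the first section, subtracting the women's counts from the totals leaves men with 5 - 4 = 1 of 38 (technical) and 12 - 9 = 3 of 15 (cotton). Women have 4/38 and 9/18.

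Logistic regression on sex and sock gives these odds ratios, women against men:
- First section: 4.1 (95% CI 1.1 to 14.8).
- Second section: 2.3 (95% CI 0.95 to 5.8).

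The crude odds ratios are (13 × 49)/(4 × 43) = 3.70 and (21 × 41)/(12 × 33) = 2.17. Their ratio is 2.17/3.70 = 0.59, with an approximate interval of 0.14 to 2.5 that ignores within-person correlation. Both odds ratios are above 1, so the reported percentages show no reversal.

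**The case against.** The strongest reply is that each sentence compares the sexes inside one section. Everyone there shared the surface, the order and the stop, so these cannot bias the comparison. That stands, and it holds for the sock comparisons too. A reader might infer that the confounding undermines the trial's sock results; it does not. The technical-cotton contrast keeps its direction and its significance in both sections.

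The reach is also small. The wording about hikes of a given length occurs in two adjacent sentences. Elsewhere the document speaks of the first and second part of the hike, and the labels of Tables 3, 4 and 7 are acceptable section labels. A reader might infer that the document gives advice by hike length. It gives none, it reports no between-section test of lesions, and its stated aim concerns sock type. The first phrase describes a distance these hikers did walk from fresh, and lacks only the surface.

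A reader might also take "temperature stabilization of 14.5 km to 29.6 km in all types of socks" as a claim that distance causes the plateau. It describes readings at route points and makes no causal statement.

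Loose English may explain the two sentences. Even so, they state a contrast by length, joined by 'However', in the paragraph that presents the regression results as predictions. The wording needs correcting whatever its origin.

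**Conclusion.** The point holds as a fault in two stated conclusions. It is not a fault in the sock comparison. The aliasing is complete: none of the between-section change can be credited to distance, and the second label misnames what was counted.

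A second fault lies in the same sentence and would survive relabelling. The claim that men are at higher risk in the second section is opposite in direction to the percentages in the Results text under Table 4. The documents do not show that the regression is wrong: a model adjusted for age and BMI could point the other way, but Table 7 gives only 90% for men, with no odds ratio, interval or p-value. Nor do the percentages show a reversal that surface or fatigue would have to explain.

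Assumptions:
- Counts are rebuilt from rounded percentages. The second-section figures fit 76 technical and 31 cotton wearers (women 38 and 16). Section 3 says both women who withdrew wore technical socks, which would leave 74 and 33, and the percentages do not fit those numbers. This needs reconciling, but the direction by sex comes from the printed percentages and does not depend on it.
- That footwear and socks came off at km 14.5 is implied by the request "to not remove their footwear or socks before examination by a podiatrist" and is not stated outright. The aliasing does not depend on it.

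**What to change.** In the text after Table 7:
- Replace the two phrases with *in the first section (asphalt)* and *in the second section (dirt, after 14.5 km on asphalt and a mid-route examination)*.
- Draw no conclusion by hike length, and state that surface, distance and order cannot be separated in this design.
- Reconcile the sex statement for the second section with the percentages under Table 4: report the adjusted odds ratio with its confidence interval and the covariates used, or withdraw the statement.

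Tables 3, 4 and 7 may keep their wording with the surface added. The temperature result may stay as a description by route point. The sock comparisons within each section stay as they are.

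The cost is wording plus output from a regression already run; no new data are needed. The downside is a narrower conclusion. Separating the factors would take a different study: randomising the order of surfaces would separate surface from section, but distance, order and the stop would stay tied unless groups walked different lengths or some skipped the mid-route examination.

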Quantitative variables depending on whether the samples were paired or independent, Friedman's test for related samples and Kruskal-Wallis was performed for independent samples, both with Bonferroni correction for multiple testing was applied. For the qualitative variables the

chi-square or Fisher's exact test with a significance level of α = 0.05 was carried out. The variables analysed by logistic regression were quantified using the ODDS Ratio (OR). The effect size for the different variables was also calculated. First, for Kruskall-Wallis tests, the variation was between 0.443 y 0.888, and for Friedman tests, the variation was between 0.336 y 0.623. Therefore, in both cases the effect size could be considered median and high.

All p-values = 0.000 are less than 1 per 1000.

Results

After completing the first part of the hike, the most frequent dermal lesions among participants were blisters and erosions.

Table 3. Prevalence of skin, muscle and nail lesions during the 0-14.5 km of the hike by sex.

(0.14 = 1)				Fen	nale					Ma	ıle		
(0-14.5 km)		Tier	ra %	Se	et %	Cott	on %	Tier	ra %	Set	%	Cott	on %
Skin lesion	%Tt.	RF	LF	RF	LF	RF	LF	RF	LF	RF	LF	RF	LF
Blister	12.8	0.0	4.0	8.0	7.7	22.2	27.8	0.0	5.3	5.3	0.0	6.7	13.3
Erosion	2.8	0.0	0.0	0.0	0.0	11.1	5.6	0.0	0.0	0.0	0.0	6.7	0.0
(0.44.5.1)				Fer	male					Ma	ıle		
(0-14.5 km)		Tier	ra %	Se	et %	Cott	on %	Tier	ra %	Set	%	Cott	on %
Muscle lesion	%Tt.	RF	LF	RF	LF	RF	LF	RF	LF	RF	LF	RF	LF
Pain due inadequate warm	21.1	23.1	27.8	8.0	7.7	27.8	27.8	10.5	15.8	10.5	0.0	13.3	13.3
Inflammation	2.8	0.0	4.2	4.0	0.0	0.0	0.0	0.0	10.5	10.5	0.0	0.0	0.0
Muscle discomfort	1.8	0.0	0.0	0.0	0.00	0.0	0.0	5.3	5.3	0.0	0.0	0.0	0.0

Km=Kilometres, %=Percentage, Tt=Total, RF=Right foot, LF=Left foot.

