None of the other dermal lesions included in the evaluation (reddened skin, urticaria, crevice and heloma) were detected. Significant differences were found between the percentage of dermal lesions in hikers wearing technical socks (6.6%) and non-technical socks (36.4%) (p-value=0.000). The women had a higher percentage of dermal lesions (23.2%) than the men (7.5%) (p-value=0.034), regardless of sock type. Moreover, the percentage of women with dermal lesions was significantly higher among wearers of non-technical socks (50%) than in wearers of technical socks (10.5% had lesion) (p-value=0.002). Particularly the women presented more blisters in both RF and LF when they wore cotton sock compared to the Tierra and Set socks (RF p-value = 0.050, LF p-value = 0.042). In the case of men, there was no difference in any of the skin lesions at 14.5 km on any foot compared to the sock used (Table 3). The most frequent muscle lesions at the end of the first part of the hike were pain due inadequate warm (21.1%), inflammation (2.8%) and muscle discomfort (1.8%). No sprains or nail disorders were detected at the end of the first part of the hike. No difference between any of muscle lesions analyzed and technical and non-technical socks were found. By sex, no differences were found regarding technical and non-technical socks or concerning the model used sock on each foot (Table 3).

Table 4. Prevalence of skin, muscle and nail lesions during the 14.5-29.6 km of the hike by sex.

(14.5-29.6 km)				Fema	ale					N	I ale		
(14.5-29.6 KM)		Tie	rra %	Set	%	Cott	on %	Tier	ra %	Se	et %	Cott	on %
Skin lesion	%Tt.	RF	LF	RF	LF	RF	LF	RF	LF	RF	LF	RF	LF
Blister	19.6	7.7	12.0	20.0	7.7	25.0	12.5	5.3	0.0	5.3	21.1	6.7	0.0
Erosion	7.5	0.0	4.0	8.0	0.0	12.5	18.8	0.0	0.0	0.0	0.0	20.0	13.3
Reddened skin	3.7	0.0	0.0	0.0	0.0	18.8	18.8	0.0	0.0	0.0	0.0	6.7	6.7
Urticaria	0.9	0.0	0.0	0.0	0.0	6.3	6.3	0.0	0.0	0.0	0.0	0.0	0.0
Crevice	0.9	0.0	0.0	0.0	0.0	0.0	0.0	0.0	0.0	0.0	0.0	6.7	0.0
Heloma	0.9	0.0	0.0	0.0	0.0	0.0	0.0	0.0	0.0	0.0	0.0	6.7	6.7
(14.5-29.6 km)			Female			Male							

		Tier	ra %	Set	t %	Cott	on %	Tier	a %	Se	et %	Cott	on %
Muscle lesion	%Tt.	RF	LF	RF	LF	RF	LF	RF	LF	RF	LF	RF	LF
Pain due inadequate warm	11.2	15.4	4.0	4.0	7.7	0.0	12.5	10.5	0.0	5.3	10.5	0.0	0.0
Inflammation	0.9	0.0	4.0	4.0	0.0	0.0	0.0	0.0	0.0	0.0	0.0	0.0	0.0
Muscle discomfort	0.9	0.0	0.0	0.0	0.0	0.0	0.0	0.0	0.0	5.3	0.0	0.0	0.0
Sprain	0.9	0.0	0.0	4.0	0.0	0.0	0.0	0.0	0.0	0.0	0.0	0.0	0.0
(14.5-29.6 km)				Fem	ale					N	Iale		

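### The unqualified statement that men are more likely than women to have muscle lesions in the first 14.5 km conflicts with Table 3, and the document does not explain the conflict

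*Combined protocol and SAP*

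**What the plan says.** Section 3 gives the denominators: "The sample comprised 109 participants (53 men and 56 women". The Results text on the first half of the hike gives the overall frequencies of muscle lesions: "pain due inadequate warm (21.1%), inflammation (2.8%) and muscle discomfort (1.8". Table 3 splits each type by sex, sock and foot.

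The text below Table 7, which introduces the logistic regression, then says that men are more likely than women to have "muscle lesions on hikes of up to 14.5 km". The muscle column of Table 7 shows 100% for male sex, a direct relation with BMI and an inverse relation with age. Section 6 says the variables in the logistic regression were quantified by odds ratios. No odds ratio, interval, p-value or covariate list is printed for the sex effect, and the sentence does not say that it is adjusted for anything.

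**The concern.** In the Table 3 row "Pain due inadequate warm", which holds most of the muscle lesions, the women's rate is above the men's in five of the six sock-by-foot cells: 23.1 v 10.5 and 27.8 v 15.8 (Tierra, right and left), 7.7 v 0.0 (Set left), and 27.8 v 13.3 on each foot (cotton). Only Set on the right foot leans towards men (8.0 v 10.5).

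The sentence below Table 7 is the document's only between-sex conclusion on muscle lesions. A reader will take it as a plain statement that men are at higher risk, although the observed rate of the main lesion is not higher in men and nothing printed reconciles the two.

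**Working it through.** **Inputs.** Totals and cell percentages come from Table 3, denominators from Table 1. Each technical-sock hiker wore Tierra on one foot and Set on the other, so left Tierra and right Set are the same people.

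| Group | Men | Women |
|---|---|---|
| Left Tierra / right Set | 19 | 25 |
| Left Set / right Tierra | 19 | 13 |
| Cotton, both feet | 15 | 18 |

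**Reproducing the printed totals.** 23/109 = 21.1% (pain), 3/109 = 2.8% (inflammation), 2/109 = 1.8% (discomfort). Each is the only integer count that fits. The sum is 23 + 3 + 2 = 28 affected hikers if nobody had two types.

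**Pain, by foot.**
- Men: right Tierra 2/19, left Tierra 3/19, right Set 2/19, left Set 0/19, cotton 2/15 and 2/15. The sum is 11 foot entries.
- Women: right Tierra 3/13, right Set 2/25, left Set 1/13, cotton 5/18 and 5/18. Left Tierra is k/25.
- The printed 27.8% is not a fraction of 25: 7/25 = 28.0% and 6/25 = 24.0%. Among denominators 13 to 25, only 5/18 gives 27.8%, which is also the value in both female cotton cells. The nearest count is k = 7, but the true count is uncertain.

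**Pain, by hiker.** In each group the number of hikers lies between max(right, left) and right + left.
- Men: (3 to 5) + 2 + (2 to 4) = 7 to 11.
- Women: (max(k, 2) to k + 2) + (3 to 4) + (5 to 10).
- Men and women must sum to 23.

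| Left Tierra count k | Women with pain | Men with pain |
|---|---|---|
| 8 | 16/56 (28.6%) | 7/53 (13.2%) |
| 7 (nearest to print) | 15-16/56 (26.8-28.6%) | 7-8/53 (13.2-15.1%) |
| 6 | 14-16/56 (25.0-28.6%) | 7-9/53 (13.2-17.0%) |
| 5 | 13-16/56 (23.2-28.6%) | 7-10/53 (13.2-18.9%) |
| 0 to 4 | 12-16/56 (21.4-28.6%) | 7-11/53 (13.2-20.8%) |

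The last row does not depend on k. Eleven male foot entries mean at most 11 men, hence at least 23 - 11 = 12 women, and 12/56 = 21.4% is still above 11/53 = 20.8%.

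**Fisher's exact test on pain.** 16 v 7: p = 0.06. 15 v 8: p = 0.16. 14 v 9: p = 0.35. 13 v 10: p = 0.64. 12 v 11: p = 1.0.

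**Any muscle lesion.** The inflammation cells (2/19 men on left Tierra and on right Set; one woman in the matching group) and the total of 3 fit 2 men and 1 woman. The discomfort cells fit 2 men. So men with any lesion number between m and m + 4, and women between w and w + 1, where m and w are the pain counts. The arrangement most favourable to men gives:
- k = 7: women 15/56 = 26.8%, men (8 + 4)/53 = 22.6%.
- k = 6: women 14/56 = 25.0%, men (9 + 4)/53 = 24.5%.
- k = 5: women 13/56 = 23.2%, men (10 + 4)/53 = 26.4%.
- k = 4 or fewer: women 12/56 = 21.4%, men (11 + 4)/53 = 28.3%.

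**The 100% in Table 7.** The largest possible number of men with any muscle lesion is 11 + 4 = 15, or 15/53 = 28.3%. The figure cannot be an observed risk.

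**The case against.** The strongest reply is that the sentence reports a logistic regression while Table 3 is crude. A crude rate and a modelled sex effect can differ in sign without either being wrong. Men were older (49 v 36 years), and age is reported as inversely related to muscle lesions, so adjustment for age would move the sex effect towards men. Men also had higher BMI (26.6 v 23.5), and BMI is reported as directly related, so adjustment for BMI would move it the other way. The net adjusted sign cannot be determined from the documents. This stands. It leaves the discrepancy unexplained, because no adjusted estimate or covariate list is printed.

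The count of five cells in six is also weaker than it looks. Right and left feet belong to the same hikers, the two cotton comparisons use the same people, 7.7 v 0.0 is one woman of 13, and one cell is arithmetically impossible. That stands too, which is why the working rests on hiker-level bounds.

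A reader might infer more: that the direction of risk has been reversed, that the wrong sex has been named, or that the regression is in error. The documents do not support this. The outcome in the sentence is any muscle lesion, and with 5 or fewer women in the doubtful cell the crude direction for that outcome can favour men. The crude pain difference is not significant at any feasible split.

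**Conclusion.** The concern holds as an unexplained discrepancy between an unqualified conclusion and the document's own table. Crude pain is more common in women whatever the count in the doubtful cell: 15 or 16 of the 56 women against 7 or 8 of the 53 men at the printed value, and between 12 and 16 women against between 7 and 11 men if the cell is unknown. Any muscle lesion is also more common in women at the printed value, but that direction is not fixed if the true count is 5 or fewer. With Fisher p from 0.06 to 1.0 for pain, neither sex is shown to be at higher risk.

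This assumes that the column of totals counts hikers, that the Table 1 denominators apply at 14.5 km, and that the cells other than left Tierra in women are correct (for inflammation, that cell's 4.2% is read as one woman).

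**What to change.** - Correct the pain entry for women, left foot, Tierra in Table 3.
- Print the observed number of men and of women with any muscle lesion at 0-14.5 km, counting each hiker once.
- In Table 7, replace the 100% for male sex with the odds ratio for sex, its confidence interval and the list of covariates in the model.
- Reword the sentence below Table 7 as an adjusted association, noting that crude pain is not higher in men. If the fitted odds ratio and its interval do not support it, withdraw the sex conclusion.

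The cost is one cross-tabulation from existing data, the output of a model already fitted, one corrected cell and one rewritten sentence.

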The qualitative variables analysed were: gender, body mass index (BMI) by rank, sock type, dermal lesions (all lesions developed during the hike, both keratopathies with keratinisation disorder and dermatopathies without keratinisation disorder), muscle lesions (all lesions developed during the hike) and nail lesions (all nail lesions developed during the hike, both traumatic and non-traumatic onychopathies). The height and weight data obtained were used to calculate BMI by rank, interpreted according to the World Health Organization classification [41] (Table 2).

Table 2. Qualitative variables and categories. BMI= Body mass index.

Qualitative variable	Category	
Gender	Male Female	
BMI	Underweight (<18.5) Normal weight (18.5-24.99) Overweight (25.0-29.9) Obese ((>30)
Sock type	Technical (Tierra) Technical (Set) Non-technical (Cotton)	
Skin lesion	Blister Injury (Erosion & chafing) Reddened skin Urticaria Crevice H	Ieloma
Muscle lesion	Pain due inadequate warm Inflammation Muscle discomfort Sprain	
Nail lesion	Onychocryptosis Subungueal hematoma	

The quantitative variables analysed were: age, body mass index (BMI), temperature of each foot measured in two aspects (plantar and dorsal), and perimeter of each foot, measured in four areas (dorsal aspect of toes, instep, heel, tibia).

5. Measuring instruments

The height range and the pace hikers was controlled with a Garmin ETREX 20X GPS (Global Positioning System). Perimeter was measured with a flexible, non-elastic tape measure (Lawton 18-0160, precision 1 mm). Weight was measured using scales (Tanita UM-076, precision 0.1kg) and height was measured using the weight rod of different scales (SECA 704, precision 1 mm).

Temperatures were taken with an infrared thermometer (FTN Medisana, precision 0.18° C), calculating the mean of the three measurements. An intra rate of the measure was done to detect the error of the measure of the temperature, obtaining an error of 0.1452.

6. Statistical tests

The data were analysed using IBM SPSS Statistics for Windows, Version 22.0 (IBM, Armonk, New York). The statistical treatment consisted of data study and cleansing, descriptive variable analysis, normality test (Shapiro-Wilks test). The studies of normality were no significant (p-values between 0.000 y 0.044).

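### The statement that non-technical socks carry the highest probability of muscle lesions in both parts of the hike is not supported by the document's own tables and comparisons

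*Combined protocol and SAP*

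**What the plan says.** After Table 7 the Results conclude: "The non-technical socks showed the highest probability of wearers suffering dermal and muscle lesions". The rest of that sentence applies the claim to the first and the second part alike. In the muscle column of Table 7, which covers 0-14.5 km only, the sock entry is 67% for the non-technical sock. No odds ratio, confidence interval, p-value or coefficient is shown, although section 6 (Statistical tests) says the regression results were quantified by odds ratios.

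Table 2 (section 4, Study variables) lists four muscle lesions: "Pain due inadequate warm Inflammation Muscle discomfort Sprain". For the first part the Results give the frequencies, in percent, as "pain due inadequate warm (21.1%), inflammation (2.8%) and muscle discomfort (1.8"; sprain did not occur. The text on the first part then says that no muscle lesion differed between technical and non-technical socks. The text on the second part says the same, overall and by sex.

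**The concern.** The effect of sock type is the purpose of the trial, so a sentence that ranks the socks on a lesion class is a main conclusion. For dermal lesions the document reports clear differences between sock types. The muscle claim is attached to the same sentence, but the direct comparisons reported for muscle lesions are null in both parts, and the regression table offers nothing for the second part. A reader of the conclusion alone would credit technical socks with preventing muscle lesions along the whole route.

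**Working it through.** **Inputs.** Table 1: 33 cotton hikers (18 women, 15 men) and 76 technical-sock hikers. Each technical-sock hiker wore "two technical socks (1 Set and 1 Tierra"), so Tierra on the left means Set on the right and the reverse. Women: 25 with Tierra left/Set right, 13 with Tierra right/Set left. Men: 19 and 19. Cell percentages and row totals come from Tables 3 and 4.

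**Method.** Count = percentage × cell size. The two feet of a pairing are joined into hikers: at least the larger of the two foot counts, at most their sum. The row total then limits the combinations. With c cotton and t technical cases, OR = [c/(n_c − c)] / [t/(n_t − t)]; p is Fisher's exact, two-sided.

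**Row totals reproduced for lesions other than pain.** Every cotton cell for inflammation, discomfort and sprain is 0.0 in both tables, and the technical cells alone give the totals.
- 0-14.5 km: inflammation 1 woman + 2 men = 3/109 = 2.8%; discomfort 2 men = 2/109 = 1.8%.
- 14.5-29.6 km: one inflammation, one discomfort, one sprain, each 1/107 = 0.9%.

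So every tabulated muscle lesion in cotton hikers is the pain item.

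**Second part, pain.** Technical feet: women 2/13 Tierra right, 1/13 Set left, 1/25 Tierra left, 1/25 Set right; men 2/19 Tierra right, 2/19 Set left, 1/19 Set right. The sum is 2+1+1+1+2+2+1 = 10. Cotton: women's left foot 12.5% = 2/16, all other cells 0. That makes 12 feet, and the row total is 11.2% of 107 = 12 hikers, so each foot is a different hiker.
- Cotton 2/31 = 6.5%, technical 10/76 = 13.2%. OR = (2/29)/(10/66) = 0.46, p = 0.50.
- Adding the three other lesions, all in technical-sock hikers, gives 10 to 13 of 76 depending on overlap, OR 0.46 down to 0.33.
- Denominators: section 3 says both women who gave up wore technical socks, which implies 33 and 74. Table 4's cotton percentages for women fit 16, not 18 (12.5% of 18 is 2.25), which implies 31 and 76. With 33 and 74 the pain figures are 6.1% and 13.5%, the same direction.

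**First part, pain.** The row is "Pain due inadequate warm 21.1 23.1 27.8 8.0 7.7 27.8 27.8 10.5 15.8 10.5 0.0 13.3 13.3", with total 21.1% of 109 = 23 hikers.
- Technical, by pairing: women 7 to 9 (Tierra left 27.8% taken as 7/25, Set right 2/25); women 3 to 4; men 3 to 5; men 2. The minimum is 7+3+3+2 = 15.
- Cotton: women 5/18 on each foot, at least 5; men 2/15 on each foot, at least 2. The minimum is 7.
- With 23 in all, the only splits are 8 cotton + 15 technical and 7 cotton + 16 technical.
- 7/33 (21.2%) vs 16/76 (21.1%): OR = (7/26)/(16/60) = 1.01, p = 1.0.
- 8/33 (24.2%) vs 15/76 (19.7%): OR = (8/25)/(15/61) = 1.30, p = 0.62.
- Any muscle lesion: adding up to 5 other technical-sock hikers gives 15-21/76 vs 7-8/33, OR 0.71-1.30.

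**Sensitivity to one cell.** The 27.8% for women's left Tierra does not fit n = 25 (7/25 is 28.0%). If it is a misprint for 5/25 or 6/25 (an assumption), the technical minimum falls to 13 at best: 10/33 (30.3%) vs 13/76 (17.1%), OR = (10/23)/(13/63) = 2.11, p = 0.13. A still smaller true count would widen this range: a count of 2 would allow 10 technical and 13 cotton hikers, OR = (13/20)/(10/66) = 4.29, p = 0.004. A split that extreme would contradict the document's own report of no sock difference in this part.

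**Side by side.** The text on each part reports no sock difference for any muscle lesion. The sentence after Table 7 claims the highest probability with non-technical socks in both parts. Table 7 contains a muscle model for the first part only.

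**The case against.** The strongest defence is that the sentence reports a regression, not a crude comparison. The model has covariates that the documents do not list, its outcome is not defined beyond muscle lesions, and the measurement form has an *Others* box under muscle lesions that is not tabulated. The 67% therefore cannot be re-derived, and an adjusted result could differ from the crude one. This stands for the first part: the tables cannot prove the 67% wrong. It does not help in the second part, for which no muscle model is shown, and it leaves the conflict with the reported null comparisons unexplained.

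Three stronger readings are tempting, and the documents do not support them.
- A reader might infer that the first-part result rests wholly on the pain item. That holds for the tabulated lesions, but it cannot be shown for a model whose outcome is undefined.
- A reader might infer that the item's name, which attributes the pain to inadequate *warm*, rules out a sock effect. The label is ambiguous and need not mean warm-up, and a between-group comparison is not invalid because a form item has a causal name.
- A reader might infer that the remaining lesions point to harm from technical socks. They number 5 lesions in 4-5 hikers in the first part and 3 lesions in 2-3 hikers in the second (p about 0.32 for 5/76 vs 0/33 and 0.55 for 3/76 vs 0/31), and 76 of 109 hikers wore technical socks. If the five first-part lesions were in different hikers, all would fall in that group by chance about 16% of the time. Nor are they hidden: Tables 3 and 4 print each item by sock, foot and sex.

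**Conclusion.** The sentence is wrong as written with respect to muscle lesions. In the second part it has no model behind it, and the tabulated data run the other way, though far from conclusively, under either set of denominators. In the first part the tabulated excess in cotton is negligible to small with the cells as printed, and not significant if the odd cell stands for 5/25 or 6/25. The document itself reports no difference.

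This rests on three assumptions: the Table 1 cell sizes apply to Table 3; the Table 4 percentages are based on 16 cotton women; and 27.8% stands for 7/25 unless stated otherwise. The finding is that the claim lacks support. It does not establish that sock type has no effect on muscle lesions. The dermal half of the sentence is not challenged here.

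**What to change.** 1. Delete the words *and muscle* from the sentence after Table 7. This needs no new analysis.
2. Keep the 67% sock entry in the muscle column of Table 7 only if the model is shown with its outcome definition (including whether *Others* counts), covariates, odds ratio and confidence interval, and is reconciled with the null comparison reported for the first part. Otherwise remove the entry. The cost is reporting a model that has already been fitted.
3. Report the pain item separately from inflammation, discomfort and sprain, by sock type and part of the hike, with counts of hikers. Keep this descriptive: with no cotton events in the other three items, an ordinary logistic model has no finite sock estimate, so recoding the outcome and refitting would not help. State what the label of the pain item means, without a claim for or against a sock cause.
4. Check the women's left Tierra cell in Table 3 against the records, and reconcile section 3 with Table 4 on which group lost two women.
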